#### ANALYSIS:

Measures of the level of glycemic control will be assessed primarily by HbA1c and secondarily by the average glucose tests results on the patient's glucose meter. Comparison of the glucose results (average, range, standard deviation, number of daily tests) between the study entry, 1 week, 1 month and 3 month follow up visits will be done. Comparison of HbA1c at entry and at 3-month follow-up will be performed. Questionnaire scores will be compared between study entry, 1 week follow up, 1 month follow up and 3-month follow-up visits for DES and Stages of Change scales. We will determine if there is a correlation between the scores on the questionnaires and measures of glucose control. We will classify study and control participants into adherent and non-adherent groups.

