#### CONFIDENTIAL

This material is the property of the NYU School of Medicine and Langone Medical Center. Do not disclose or use except as authorized in writing by the study sponsor

Use of continuous glucose monitoring system with intensive feedback in adolescents with poorly controlled type 1 diabetes  
Version Date: 04/26/2018

Dichotomizing participants into adherent and non-adherent:

Study subjects will receive points for calibrating the CGM device and for successfully completing phone contact with the pediatric diabetes team. The patient will receive 2 points for calibrating the device 2 times/day for at least 5 days, 1 point for calibrating the device 2 times on at least 3 days and 0 points for calibrating any less. Similarly the patient will receive 2 points for completing successful phone contact with study personnel for at least 5 days, 1 point for completing phone contact on at least 3 days and 0 point for contact any less than mentioned before. The two scores will be added to get a total score. Patients with scores 3-4 will be classified as adherent and scores 0-2 will be classified as non-adherent. Control subjects who complete 4 or more phone calls on different days will be classified as adherent and those who complete fewer phone calls will be classified as non-adherent.

Statistical methods:

Demographic data will be tabulated. Statistical analysis of questionnaires will be done according to published standards. The paired t-test will be used for comparisons involving stages of change score.

Independent variables will include the empowerment score, average glucoses, HbA1c and whether the subjects fall into the adherent vs. non-adherent groups. Dependent variables include glucose level(s) and stage of change. We will analyze the 7 day average glucose by meter download and categorize the results in terms of change: No change (-15 to + 15), Higher ( $\geq + 15$ ) or Lower ( $\leq -15$ ). We will analyze the HbA1c and categorize the results in terms of change: No change ( $> -0.5$  to  $+ 0.5$ ), Higher ( $\geq + 0.5$ ) or Lower ( $\leq -0.5$ ). Stages of change (Appendix A) will be categorized as unchanged, improved or worsened. In addition, descriptive statistics including quality of life, diabetes knowledge scale, and demographic variables will be tabulated.

Statistical Analysis for sensor study:

Questionnaires:

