Daily Phone Log: (Appendix H): Scoring will be done for each day of the initial week of the study, in both CGM intervention group, and control group based on the following: Study subjects will receive points for calibrating the CGM device and for successfully completing phone contact with the pediatric diabetes team. The patient will receive 2 points for calibrating the device 2 times/day for at least 5 days, 1 point for calibrating the device 2 times on at least 3 days and 0 points for calibrating any less. Similarly the patient will receive 2 points for completing successful phone contact with study personnel for at least 5 days, 1 point for completing phone contact on at least 3 days and 0 point for contact any less than mentioned before. The two scores will be added to get a total score. Patients with scores 3-4 will be classified as adherent and scores 0-2 will be classified as non-adherent. Control subjects who complete 4 or more phone calls on different days will be classified as adherent and those who complete fewer phone calls will be classified as non-adherent.

The distribution of the data will be assessed using the Kolmogorov-Smirnov test. All categorical variables will be presented as mean +standard deviation. For categorical variables the differences between the compliant and non-compliant groups will be assessed using the Mann Whitney or rank order Wilcoxon test based on normality. For categorical variables independent sample t test will be used. Univariate analysis will be used to establish correlation between variables of interest.

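### The adherent versus non-adherent comparison covers both arms, but no stratification or adjustment by randomised arm is stated

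*Combined protocol and SAP*

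**What the plan says.** The ANALYSIS section states: "We will classify study and control participants into adherent and non-adherent groups". The rule then depends on the arm (paragraph on dichotomizing participants, repeated under Daily Phone Log, Appendix H):

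- CGM arm: 0 to 2 points for calibration days plus 0 to 2 points for phone-contact days. "Patients with scores 3-4 will be classified as adherent and scores 0-2 will be classified as non-adherent".
- Control arm: phone calls only. "Control subjects who complete 4 or more phone calls on different days will be classified as adherent".

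Under Daily Phone Log, "Scoring will be done for each day of the initial week of the study, in both CGM intervention group, and control group".

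Under Statistical methods, "Independent variables will include the empowerment score, average glucoses, HbA1c and whether the subjects fall into the adherent vs. non-adherent groups". The next sentence adds: "Dependent variables include glucose level(s) and stage of change". Randomised arm is not named among the independent variables.

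For testing, the last paragraph on Appendix H says that "the differences between the compliant and non-compliant groups will be assessed using the Mann Whitney or rank order Wilcoxon test", depending on normality, and gives an independent-sample t test as the other option. Both tests are introduced as being for categorical variables, so it is unclear which outcomes are meant. The paragraph ends: "Univariate analysis will be used to establish correlation between variables of interest". No sentence restricts, stratifies or adjusts the adherence comparison by arm.

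**The concern.** A two-sample test of adherent against non-adherent participants, with the arms combined, compares two groups that may contain different shares of CGM participants. If the CGM intervention also shifts the outcome, part of that shift appears as an adherence difference, or cancels a real one.

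The documents show two possible sources of unequal adherence:

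- **The rules differ.** A CGM participant with calls on all 7 days but fewer than 3 calibration days scores 2 and is non-adherent; a control with the same calls is adherent. Conversely, a CGM participant with 3 phone days and 5 calibration days scores 3 and is adherent; a control with 3 phone days is not.
- **Call completion may differ.** METHODS and CONSENT describe the daily calls together with wearing the device. Calls to controls appear only through the scoring rule and the log.

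Different rules are neither necessary nor sufficient for the problem. The cause that can be fixed is the absence of arm from the analysis. At stake is the reading of a named explanatory variable: the trial could report that engagement goes with better glucose or stage of change when the difference belongs to the device arm, or miss a real association.

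**Working it through.** The plan gives no figure to reproduce here: it states no adherence rate, SD, arm effect or power calculation.

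**Inputs from the documents:** 40 CGM and 20 control participants (SUBJECTS), a 7-day scoring week, and the two adherence rules above.

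**Assumed inputs:** daily probabilities of completing a call (p) and of calibrating twice (q), with days independent, and calls independent of calibration unless noted.

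**Step 1. Proportion adherent.** Calls ~ Binomial(7, p); calibration days ~ Binomial(7, q).

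- Control: c = P(calls ≥ 4)
- CGM: g = P(calls ≥ 5) × P(cal ≥ 3) + P(calls 3 or 4) × P(cal ≥ 5)

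With all rates 0.6: c = 0.710 and g = 0.4199 × 0.9037 + 0.4838 × 0.4199 = 0.583.

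**Step 2. Fraction of the arm effect carried into the contrast.** This is the CGM share among the adherent minus the CGM share among the non-adherent:

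40g/(20c + 40g) − 40(1 − g)/(60 − 20c − 40g)

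With all rates 0.6: 0.621 − 0.742 = −0.121. A 0.5 SD arm effect would then give a spurious adherence difference of 0.5 × (−0.121) = −0.06 SD.

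**Step 3. False-positive rate.** Simulated trials with a normal outcome (SD 1), no adherence effect, and an arm effect of 0.5 or 1.0 SD, tested by unadjusted Mann-Whitney at 5%. There were 6,000 trials per setting (Monte Carlo standard error about 0.3 points near 5%), except 3,000 in rows marked *.

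| Control calls | CGM calls | Calibration | c | g | Carried fraction | Error, 0.5 SD | Error, 1.0 SD |
|---|---|---|---|---|---|---|---|
| 0.8 | 0.8 | 0.8 | 0.967 | 0.970 | +0.03 | 4.9%* | 4.7%* |
| 0.6 | 0.6 | 0.7 | 0.710 | 0.721 | +0.01 | 4.4%* | 5.1%* |
| 0.6 | 0.6 | 0.6 | 0.710 | 0.583 | −0.12 | 5.2% | 7.3% |
| 0.6 | 0.6 | 0.6, same days as calls | 0.710 | 0.420 | −0.26 | 7.4% | 14.1% |
| 0.6 | 0.6 | 0.9 | 0.710 | 0.891 | +0.29 | 6.7% | 12.0% |
| 0.4 | 0.6 | 0.6 | 0.290 | 0.583 | +0.26 | 7.1% | 14.0% |
| 0.5 | 0.7 | 0.7 | 0.500 | 0.838 | +0.38 | 9.7% | 20.6% |
| 0.7 | 0.5 | 0.5 | 0.874 | 0.299 | −0.51 | about 16%* | not run |
| 0.6 | 0.6 | 0.3 | 0.710 | 0.162 | −0.54 | 16.0% | 43.7% |

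**Step 4. With arm in the analysis.** In the six settings without an asterisk, a linear model with adherence and arm gave 4.8% to 5.5%. A Wilcoxon test stratified by arm gave about 4% to 6%.

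**Step 5. Would a common rule be enough?** Applying the 4-day phone rule to both arms removes the carry-over when call rates are equal, but not otherwise:

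- controls 0.5, CGM 0.7: +0.44
- controls 0.4, CGM 0.6: +0.38
- controls 0.7, CGM 0.5: −0.35

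**Step 6. Precision cost of the arm term.** The standard error is multiplied by 1/√(1 − r²), where r² = carried fraction × (g − c):

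- all rates 0.6: r² = −0.121 × (0.583 − 0.710) = 0.015, factor 1.008
- controls 0.5, CGM 0.7: r² = 0.377 × (0.838 − 0.500) = 0.127, factor 1.07
- calibration 0.3: r² = −0.539 × (0.162 − 0.710) = 0.295, factor 1.19

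**The case against.** Pooling is inferred. The plan never says that the arms are combined, and separate rules for each arm would also fit within-arm use. This is true, but an unstated choice leaves the analyst free to decide after seeing the data, and arm is missing from the listed independent variables.

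The distortion also needs both an arm effect and unequal adherence, and it is negligible in several plausible settings. The 43.7% figure requires calibration on 30% of days and a 1.0 SD arm effect. The documents give no support for an effect that large: the device is worn for about a week, and the protocol's background notes that HbA1c did not improve in adolescents placed on CGM. This stands as a limit on size. It does not remove the point, because the trial is designed to look for an arm difference and the adherence rates are unknown.

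Lower call completion among controls is conjecture, since the plan does log and score their calls. That too stands, but the rules alone produce imbalance when call rates are equal.

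The simulation used a normal outcome, whereas stage of change is to be categorised as improved, unchanged or worsened. The error rates therefore do not transfer exactly to that outcome, although the mechanism does.

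Finally, an additive arm term still averages two meanings of adherence into one coefficient. Within-arm results avoid this, but the control groups are small.

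**Conclusion.** The concern holds. As written, the plan puts both arms under one adherence label and compares its groups without reference to arm, so the contrast is confounded by arm whenever adherence and outcome both differ between arms. Under the assumed rates, the false-positive rate runs from nominal to about 16% at a 0.5 SD arm effect, and to about 44% in the most extreme setting at 1.0 SD. In moderate settings the distortion is small, and its direction cannot be predicted.

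These figures rest on assumed call and calibration rates, assumed arm effects, a normal outcome and pooled arms. The consequence is confined to the adherence analyses; the entry to 3-month HbA1c comparison does not use the adherence label. This is an inexpensive improvement that should be made, not a threat to the trial's main glycaemic measure.

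**What to change.** Add a few sentences to the analysis section:

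1. Every adherent versus non-adherent comparison is made within arm or adjusted for arm, by a Wilcoxon test stratified by arm or a model with an arm term. Name the outcomes compared.
2. Adherent and non-adherent counts are tabulated by arm.
3. The comparison is labelled exploratory. Adherence is measured after randomisation, so even the adjusted contrast is an association and not an effect of engagement.
4. Optionally, a phone-days measure common to both arms, taken from the existing log, is used as a sensitivity analysis with the same arm adjustment.

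No new data are needed. The arm term widens the standard error of the adherence contrast by about 1%, 7% or 19% in the three settings worked above, before any gain from lower residual variance. Within-arm groups will be small: among 20 controls, about 14 adherent and 6 non-adherent at a daily call rate of 0.6 (20 × 0.710 = 14.2), and 19 and 1 at 0.8 (20 × 0.967 = 19.3). The within-control comparison may therefore have to be descriptive.

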#### SUBJECTS:

Sixty adolescents, ages 13-22 years, with type 1 diabetes and an HbA1c  $\geq 8\%$  who are also naive to CGMS or who have not used a CGMS in at least six months use will be recruited from the diabetes outpatient population followed at Bellevue Hospital, Lutheran Hospital, Woodhull Hospital, and the NYU Fink Pediatric Ambulatory Care Center. Forty subjects will be randomly assigned to the CGMS group and 20 subjects will be assigned to the control group.

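### The adherence contrast compares groups formed by self-selected week-1 behaviour without adjusting for entry status, so pre-existing differences could appear as an association with adherence

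*Combined protocol and SAP*

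**What the plan says.** SUBJECTS sets the allocation: "Forty subjects will be randomly assigned to the CGMS group and 20 subjects will be assigned to the control group". Adherence is observed after that. For the phone log the plan states "Scoring will be done for each day of the initial week of the study". In the CGMS arm, points for calibration and for completed phone contact are added: "Patients with scores 3-4 will be classified as adherent and scores 0-2 will be classified as non-adherent". The control arm has its own rule: "Control subjects who complete 4 or more phone calls on different days will be classified as adherent".

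Under Statistical methods, the independent variables include "whether the subjects fall into the adherent vs. non-adherent groups", listed beside the empowerment score, average glucose and HbA1c. Glucose and stage of change are the dependent variables.

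The last paragraph of ANALYSIS names the tests: "the differences between the compliant and non-compliant groups will be assessed using the Mann Whitney or rank order Wilcoxon test", then "For categorical variables independent sample t test will be used", then "Univariate analysis will be used to establish correlation between variables of interest". No regression, analysis of covariance, stratification or covariate is named anywhere in the section.

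Entry values enter in one way. Glucose and HbA1c are sorted into no change, higher or lower, and stage of change into improved, unchanged or worsened.

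**The concern.** Adherence is chosen by the participant and is not randomised. An adolescent who arrives more motivated, or in better control, may be more likely both to take the calls and calibrate, and to have a later stage of change and lower glucose at follow-up whatever happened in week 1. Analysing one arm at a time does not help, because the self-selection operates within each arm.

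This matters here because motivation is the trial's subject. The AIM section hypothesises that feedback and self-efficacy influence stage of change, and the introduction presumes that earlier null results in adolescents reflect inconsistent use. A difference between adherent and non-adherent participants would fit that account easily, even if adherence only marked who was already doing better. The entry measures needed to separate the two explanations (Stages of Change, the empowerment scale, HbA1c and the meter download) are all collected at the first visit.

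**Working it through.** **Inputs from the documents.** 40 CGMS and 20 control participants (40 + 20 = 60, as in the Study Summary); adherence scored in week 1; unadjusted rank or t tests. The documents give no significance level, power, SD, dropout or adherent proportion, so there is no planned figure to reproduce for this contrast.

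**Inputs assumed.** CGMS arm only, split 20:20; adherence has no effect; two-sided 0.05; entry outcome E in SD units, with higher meaning better; follow-up Y = 0.7E + noise, total variance 1; correlation r between E and a latent tendency to adhere of 0.2 / 0.4 / 0.6.

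**Size of the spurious difference.** Splitting the latent tendency at its median gives an entry difference of 2r√(2/π) = 1.596r.
- Follow-up value: 0.7 × 1.596r = 1.117r, that is 0.22 / 0.45 / 0.67 SD in favour of adherence.
- Change from entry: (0.7 − 1) × 1.596r = −0.479r, that is −0.10 / −0.19 / −0.29 SD, against adherence (regression to the mean).

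Simulation gives 0.22 / 0.44 / 0.65 and −0.09 / −0.18 / −0.28.

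**False-positive rates in the same model (simulated).**

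| Analysis | r = 0.2 | r = 0.4 | r = 0.6 |
|---|---|---|---|
| Mann-Whitney, follow-up value | 10% | 29% | 55% |
| Change from entry, unadjusted | 6% | 11% | 21% |
| Regression adjusted for entry value | about 5% | about 5% | about 5% |

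At r = 0 the unadjusted tests hold about 5%. On change scores, false positives that favour adherence are only 1.0% / 0.1% / 0.05%.

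**Hand check at r = 0.4 (normal approximation).**
- Follow-up: within-group variance 1 − (0.447/2)² = 0.950; SE = √(0.950 × 2/20) = 0.308; 0.447/0.308 = 1.45; Φ(1.45 − 1.96) = 0.31.
- Change: total variance 2(1 − 0.7) = 0.6; within-group 0.6 − (0.191/2)² = 0.591; SE = 0.243; 0.191/0.243 = 0.79; Φ(0.79 − 1.96) = 0.12.

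Both agree with the simulated rates.

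**Motivation separated from the outcome.** The model above treats entry motivation and entry outcome as one variable, which flatters the adjustment. A second model keeps them apart. It assumes a path of 0.6 from entry to 3-month outcome, motivation acting on both entry level and later value (0.3 each), adherence-motivation correlation 0.3 / 0.5 / 0.7, n = 40 and no adherence effect.

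| Analysis | 0.3 | 0.5 | 0.7 |
|---|---|---|---|
| Mann-Whitney, 3-month value | 11% | 20% | 39% |
| Mann-Whitney, change | 6% | 8% | 13% |
| Adjusted for entry outcome only | 8% | 13% | 27% |
| Adjusted for entry outcome and entry motivation | 5% | 4% | 6% |

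Here the change score errs in favour of adherence (0.08 / 0.14 / 0.20 SD). If motivation acts only on the entry level, the change score errs against it (0.06 to 0.23 SD). The direction on change scores therefore depends on facts the documents do not contain. The last row assumes that motivation is measured without error.

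**The case against.** The plan does not ignore entry values. It categorises glucose, HbA1c and stage of change as change from entry, compares entry with follow-up visits, and lists the empowerment score, glucose and HbA1c as independent variables beside adherence. Its language is correlational, and no section says that adherence causes improvement. The final paragraph also does not say whether its tests apply to follow-up or change values, so the largest rates above rest on one reading of it. With 40 participants and an unknown adherent split, added covariates could make a model unstable.

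Much of this stands, and it limits the point. A reader might infer that the plan discards entry data, that the bias must favour adherence, or that the sponsor will report adherence as beneficial. The documents support none of these: entry values are partly used, the bias on change scores can run either way, and no causal reading is stated. A reader might also take this to be the trial's main group comparison, since no two-sample test is assigned to CGMS versus control. That rests on a garbled paragraph that gives both the rank test and the t-test to categorical variables, while AIM concerns CGMS use with feedback.

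What the objection does not remove is the gap itself. No model joins the listed variables, the change categories are not tied to the adherence tests, and nothing in the comparison accounts for entry motivation.

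**Conclusion.** The point holds as a weakness in a secondary, non-randomised contrast. Adherence groups formed by self-selected week-1 behaviour are to be compared without covariates, so pre-existing differences could be read as an association with adherence.

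The size depends wholly on assumed inputs. In the first model the unadjusted false-positive rate runs from about 10% to 55% on follow-up values and from about 6% to 21% on change scores, against a nominal 5%; with no link between entry status and adherence there is no inflation. These figures show that the problem can be material. They do not predict its size in this trial. Adjusting for the entry outcome alone is not enough if motivation also drives later change, and adjusting for both works only as well as motivation is measured. The five-item stage questionnaire was written for this study, so some confounding will remain.

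**What to change.** For this contrast, replace the two-sample tests with a regression within the CGMS arm of the follow-up value on adherence, the entry value of the same outcome, and entry stage of change. Use a linear model for HbA1c, meter glucose and the stage score, and an ordinal model if stage category is the outcome. Where stage is itself the outcome, the two entry covariates are the same variable.

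State that the result is an exploratory association and that residual confounding remains because entry motivation is measured imperfectly.

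The cost is analysis wording, one or two degrees of freedom at n = 40, and a more cautious conclusion. No new data are needed.

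### The closing test paragraph assigns every summary and test to categorical variables, leaving continuous HbA1c without a between-group test, CGMS versus control without any stated test, and entry-to-3-month HbA1c without a named test

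*Combined protocol and SAP*

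**What the plan says.** The test rules stand at the end of the ANALYSIS section, after the Daily Phone Log (Appendix H) item. A distribution check comes first: "The distribution of the data will be assessed using the Kolmogorov-Smirnov test". Three sentences on summaries and tests follow, and each names categorical variables:

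- Summary: "All categorical variables will be presented as mean +standard deviation".
- Rank test: "the differences between the compliant and non-compliant groups will be assessed using the Mann Whitney or rank order Wilcoxon test based on normality".
- t-test: "For categorical variables independent sample t test will be used".

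No sentence in that paragraph assigns a summary or a group test to continuous variables.

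Earlier, the opening of ANALYSIS states "Measures of the level of glycemic control will be assessed primarily by HbA1c" and then "Comparison of HbA1c at entry and at 3-month follow-up will be performed". Meter results (average, range, SD, tests per day) are to be compared "between the study entry, 1 week, 1 month and 3 month follow up visits will be done". None of these statements names a test. Statistical methods names one paired test: "The paired t-test will be used for comparisons involving stages of change score". The same subsection sorts change in HbA1c and in meter glucose into lower, no change and higher, with no test attached. SUBJECTS sets the allocation at 40 to CGMS and 20 to control.

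**The concern.** Mean and SD, a normality check and a t-test belong to continuous data. Assigned to categories, they give an analysis rule that is wrong if followed, which is more than a missing detail. The variables that need those methods, HbA1c and meter glucose as measured, are left out.

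The paragraph also names only compliance groups for a test. Compliance is observed after randomisation, so comparing those groups does not estimate the effect of assignment to CGMS. The 2:1 randomisation serves a CGMS-versus-control comparison, and the plan attaches no test to it.

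At stake is how much choice is left until the data are in hand. The trial is open-label with 60 participants, up to four visits, several outcomes and two possible groupings (arm and adherence). An analyst could not tell from the text which test, groups or scale apply to HbA1c.

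**Working it through.** **Text check.** There is no figure in the plan to reproduce: it gives N = 60 (40:20) but no alpha, power, effect size or SD. The statements on each item, side by side:

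| Item | Test named | Groups or visits named |
|---|---|---|
| Categorical variables, rank sentence | Mann-Whitney or Wilcoxon | Compliant vs non-compliant |
| Categorical variables, t-test sentence | Independent-sample t-test | None in the sentence |
| Stages of change score | Paired t-test | Pair of visits not named |
| HbA1c, entry vs 3 months | None | Visits named, arms not |
| Meter glucose across visits | None | Four visits named, arms not |
| Continuous HbA1c or glucose between groups | None | None |
| Any outcome, CGMS vs control | None | None |

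**Can the wording be repaired by inference?** Three readings are possible.

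1. *Literal.* Two consecutive sentences give the same variable type two different tests. Categories get a mean and SD, although the Demographics item reports sex as percentages. Continuous HbA1c and meter glucose have no between-group test.
2. *Rank test for ordered classes, t-test for continuous variables.* This is usable, but the normality condition has nothing to decide. Mann-Whitney and the between-group Wilcoxon are both rank tests, so normality cannot select one over the other. Continuous data that are not normal have no alternative.
3. *Continuous throughout.* The distribution check, rank test and t-test then form an ordinary normality rule, but the three-level change classes have no named between-group test.

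The plan's own usage does not settle it. The Stages of Change item in Statistical Analysis for sensor study uses the word both for a score reported with mean and SD and for the stage classes.

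Two gaps remain under all three readings: no stated test of CGMS versus control, and no named test for HbA1c from entry to 3 months or for meter glucose between visits.

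**Size of one consequence.** A literal reader could test only the three-level HbA1c class. All inputs except the arm sizes and the class limits of ±0.5 are assumptions: a true difference in change of 0.5 (means −0.5 and 0), normal data, SD of change 0.8, 1.0 or 1.5, two-sided 0.05, 20,000 simulated trials per setting.

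Hand check of the t-test: SE = SD × √(1/40 + 1/20) = SD × 0.274, critical value about 2.00 on 58 df, power ≈ Φ(0.5/SE − 2.00).

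- SD 0.8: 0.5/0.219 = 2.28; Φ(0.28) = 0.61
- SD 1.0: 0.5/0.274 = 1.83; Φ(−0.18) = 0.43
- SD 1.5: 0.5/0.411 = 1.22; Φ(−0.78) = 0.22

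Simulated power, 40 vs 20:

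| SD of change | t-test, continuous | Mann-Whitney, continuous | Rank test, three-level class | t-test minus class |
|---|---|---|---|---|
| 0.8 | 0.614 | 0.592 | 0.520 | 0.094 |
| 1.0 | 0.435 | 0.417 | 0.364 | 0.071 |
| 1.5 | 0.222 | 0.213 | 0.182 | 0.040 |

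Using the class alone costs about 4 to 9 points. Choosing between the t-test and Mann-Whitney on continuous change moves power by only 1 to 2 points (0.022, 0.018, 0.009).

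**The case against.** The strongest reply is that this is a slip for *continuous*, which any statistician would correct. That is probably right for some of the sentences. But the text does not show which ones, and each plausible correction leaves a different gap.

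Other points on that side limit how far the concern goes:

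- A reader might infer that HbA1c has no between-group test in any form. The documents do not support that. The three-level HbA1c class is categorical, so a literal reading gives it a rank test between compliant and non-compliant participants. The gap concerns HbA1c as a continuous value, and the randomised arms.
- A reader might infer that the t-test has no groups at all. The preceding sentence names the compliance groups, and these plausibly carry over. The firmer point is that CGMS versus control is named nowhere.
- A reader might infer that the independent-sample t-test would be used on before/after data, at a large loss of power. Nothing in the plan says so, and the one within-person score with an assigned test gets a paired one.
- The gap might be extended to the DES and PHQ-2 before/after comparisons. Statistical methods refers questionnaire analysis to published standards. That names no test and may mean only scoring, but it partly covers them. It cannot cover HbA1c or meter glucose.
- HbA1c is first among the glycemic measures, not declared the primary endpoint of the trial. The AIM concerns motivation and behavior, and Statistical methods also lists HbA1c as an independent variable.

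None of these supplies a test for continuous HbA1c between arms or from entry to 3 months.

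**Conclusion.** The concern holds in this form. The paragraph misassigns its summaries and tests to categorical variables. As written, continuous HbA1c and meter glucose have no between-group test, no test is stated for CGMS versus control, and the HbA1c and meter-glucose comparisons between visits have no named test. These conclusions rest on the text alone.

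The only figure offered, a loss of about 4 to 9 points of power, rests on assumed effect and SD values. It arises from the categorisation in Statistical methods and is attributable to the closing paragraph only if that paragraph is read literally. The main reason to act is that the choice of test, groups and scale is left open until after the data are seen. This should be corrected before analysis. It is a fault in specification and does not show that the trial's results would be invalid.

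**What to change.** Rewrite the paragraph by variable type:

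- **Continuous variables** (HbA1c, meter glucose, scale scores): report mean and SD. Compare change between CGMS and control on the continuous scale with one test named in advance, for example a t-test, with Mann-Whitney as a sensitivity check and not as a data-driven replacement. For within-person change use a paired test and name the visit pair, since meter glucose and DES are recorded at four visits.
- **Ordered three-level classes** (HbA1c, glucose, stage movement): report counts and percentages with a rank-sum test, stated to be secondary to the continuous analysis where one exists.
- **Unordered variables:** report counts and percentages, with Fisher's exact or chi-square only where groups are compared.

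For every test, state whether it compares randomised arms, adherence groups or visits within person. The cost is one paragraph of wording, with no new data or visits.
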